9.1.14 QOL assessment

PDQ-39 is a self-administered questionnaire for QOL. Prior to the assessment, subjects will be provided instructions on how to record PDQ-39 and assess QOL during 1 month prior to the day of the assessment. Answers to all questions will be documented in the CRF.

9.1.15 Documentation of Screen Failure

The investigator should complete the (e)CRF for the subject who signed the informed consent and withdrawn from the study before randomization.

For subjects discontinued the study before the initiation of the investigational drug in this study, the date of signing informed consent, date of birth, sex, eligibility, reason for withdrawal, AE assessment (if any, it must be collected as an AE occurred in the preceding study), concomitant medications, and the date of the last physical examination/evaluations must be recorded in the (e)CRF.

The primary reason for screen failure is recorded in the (e)CRF using the following categories:

- PTE/AEs
- Did not meet inclusion criteria or did meet exclusion criteria <specify reason>.
- Significant protocol deviation.
- Lost to follow-up.
- Voluntary withdrawal <specify reason>.
- Study termination.
- Other <specify reason>.

Subject numbers assigned to subjects who fail screening should not be reused.

9.1.16 Documentation of Study Entrance

Only subjects who meet all of the inclusion criteria and none of the exclusion criteria are eligible for entrance into the study. If the subject is found to be not eligible for the study, the investigator or sub-investigator should record the primary reason for failure on the applicable (e)CRF.

9.2 Monitoring Subject Treatment Compliance

Subjects will be instructed to bring unused investigational drugs and blister sheets to the site at each study visit. Also, compliance of the study medication from the last study visit will be checked by the investigator or sub-investigator.

All subjects should be instructed about the dosing requirement during study contacts. If a subject is persistently noncompliant with the sponsor-supplied drugs (50% of the allocated medication for the period since the last visit), it may be appropriate to withdraw the subject from the study. The authorized study personnel conducting the re-education must document the process in the subject source records.

9.3 Schedule of Observations and Procedures

The schedule for all study-related procedures for all evaluations is shown in Appendix A. Assessments should be completed at the designated visit/time point(s).

9.3.1 Study Entrance/Week 26 in Treatment Period

The subject informed consent must be obtained before initiation of tests/observations/evaluations scheduled at Week 26 (VISIT 8).

Subjects will be screened in accordance with predefined inclusion and exclusion criteria as described in Section 7.0, and subjects whose eligibility is confirmed will be enrolled in this study. See Section 9.1.15 for procedures for documenting screening failures.

Procedures to be completed at Week 26 (VISIT 8; Day 175 - 189) include:

- Dispense study medication

9.3.2 Treatment Period (Weeks 29, 32, 36, 40, and 46)

9.3.2.1 Week 29 (Treatment Period)

Week 29 (VISIT 9; Day 196-210) include:

- Physical Examination Procedure
- Vital Sign Procedure

CONFIDENTIAL

- Documentation of Concomitant Medications
- Clinical laboratory tests (including pregnancy test for female subjects of child bearing potential)
- AE assessment
- Compliance of study medication
- Dispense investigational drug

9.3.2.2 Week 32 (Treatment Period)

Procedures to be completed at Week 32 (VISIT 10; Day 217-231) include:

- Physical Examination Procedure
- Vital Sign Procedure
- Documentation of Concomitant Medications
- Clinical laboratory tests (including pregnancy test for female subjects of child bearing potential)
- MDS-UPDRS
- AE assessment
- Compliance of study medication
- Dispense investigational drug

9.3.2.3 Week 36 (Treatment Period)

Procedures to be completed at Week 36 (VISIT 11; Day 245-259) include:

- Physical Examination Procedure
- Vital Sign Procedure
- Documentation of Concomitant Medications
- MDS-UPDRS
- AE assessment
- Compliance of study medication
- Dispense investigational drug

9.3.2.4 Week 40 (Treatment Period)

Week 40 (VISIT 12; Day 273-287) include:

- Physical Examination Procedure
- Weight
- Vital Sign Procedure
- Documentation of Concomitant Medications

CONFIDENTIAL

- Clinical laboratory tests (including pregnancy test for female subjects of child bearing potential)
- ECG Procedure
- MDS-UPDRS
- QOL
- AE assessment
- Compliance of study medication
- Dispense investigational drug

9.3.2.5 Week 46 (Treatment Period)

Procedures to be completed at Week 46 (VISIT 13; Day 315-329) include:

- Physical Examination Procedure
- Vital Sign Procedure
- Documentation of Concomitant Medications
- Clinical laboratory tests (including pregnancy test for female subjects of child bearing potential)
- MDS-UPDRS
- AE assessment
- Compliance of study medication
- Dispense investigational drug

9.3.3 Week 52 (Treatment Period) or Early Termination

The following procedures will be performed in the last visit scheduled at Week 52 in the treatment period (VISIT 14; Day 357 - 371). For subjects who started the investigational drug administration in this study and are withdrawn from the study before the last visit at Week 52, the procedures scheduled at Week 52 should be performed within 7 days from the termination of study medication (the last administration day is defined as day 0), whenever possible.

- Physical Examination Procedure
- Skin examination
- Weight
- Vital Sign Procedure
- Documentation of Concomitant Medications
- Clinical laboratory tests (including pregnancy test for female subjects of child bearing potential)

- ECG Procedure
- MDS-UPDRS
- QOL
- AE assessment
- Compliance of study medication

For all subjects receiving study medication, the investigator must complete the End of Study (e)CRF page.

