6.0 STUDY DESIGN AND DESCRIPTION

6.1 Study Design

Patients will make a total of 7 visits in this study, i.e., at Weeks 26, 29, 32, 36, 40, 46 and 52 of the treatment period, to undergo designated tests, observations, and assessments.

[figure not shown]
This is a multicenter, open-label, long-term, extension, phase 3 study to evaluate the safety and efficacy of long-term administration of TVP-1012 at 1 mg for another 26 weeks in patients with early Parkinson's disease who have completed the 26-week treatment period in the preceding TVP-1012/CCT-001 study.

Among participants of the TVP-1012/CCT-001 study, those consenting to participate in this study prior to undergoing the tests, observations, and assessments at Week 26 of the treatment period (VISIT 8) in the preceding study, and fulfilling the eligibility criteria will be enrolled in this study. From the day after the VISIT 8 of the preceding study, subjects will receive TVP-1012 1 mg once daily for 26 weeks in an unblinded manner.

The visit numbers in this study will be continued from the preceding study, and the study visit week will be counted from the start of the treatment period in the preceding study.

This study will be conducted in the same study sites as those of the preceding study (55 sites) and the number of subjects to be enrolled in this study is estimated to be 182 subjects after considering dropouts in the preceding study.

Schematic of Study Design is included as Figure 6.a. A schedule of study procedures is listed in Appendix A.

V: VISIT

* Informed consent for this study must be obtained prior to tests, observations, and assessments at Week 26 of the treatment period in the preceding study. Those who consent to participate in this study and fulfilling the eligibility criteria will be enrolled in this study. Subjects will start dosing from the day after the VISIT 8.

Figure 6.a Schematic of Study Design

CONFIDENTIAL

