## Glossary

- Descriptive statistics:

Number of subjects, mean, standard deviation, maximum, minimum, and quartiles

- MAV:

Markedly Abnormal Value

- Treatment groups in the preceding study:

TVP-1012 1 mg and placebo groups in the preceding study. However, they are shown as “1 mg ->1 mg group” and “P ->1 mg group” respectively in this statistical analysis plan.

- Study drugs for treatment period in both studies:

Study drug for treatment period in the previous study and study drug in this study

- Number of days after administration (days):

- A) For the analyses based on the data after administration of TVP-1012

The day before the day of first TVP-1012 administration is shown as Day -1 and the day of first TVP-1012 administration as Day 1. That is, shown as follows:

[If the treatment group in the preceding study is 1 mg ->1 mg group]

Day before the day of first study drug administration for the treatment period in the preceding study:	Day -1
Day of first study drug administration for the treatment period in the preceding study:	Day 1

[If the treatment group in the preceding study is P ->1 mg group]

Day before the day of first study drug administration in this study:	Day -1
Day of first study drug administration in this study:	Day 1

- B) For the analyses based on the data after study drug administration for the treatment period in the preceding study

The day before the day of the first study drug administration for the treatment period in the preceding study is shown as Day -1 and the day of the first study drug administration for the treatment period in the preceding study as Day 1.

- Number of days after the end of administration (days):

Day 1 is defined as the day following the later of “day of the last study drug administration for the treatment period in the preceding study” or the “day of the last study drug administration in this study.”

- Protocol Deviations:

Protocol deviations in this study, unless otherwise specified.

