### Definition of Visit Window

#### A) For the analyses based on the data after administration of TVP-1012

For each test, observation, and evaluation items, evaluable data (i.e., non-missing and acceptable according to the Handling Rules for Analysis Data) will be handled according to the following rules. However, the number of days after administration and number of days after the end of administration will be the contents of “For the analyses based on the data after administration of TVP-1012” in the Glossary.

Among the evaluation points, at points other than at the end of administration, evaluable data within the visit window will be used. If more than one evaluable data lies within the same visit window, the examinations, observation, and assessments with the Study Time closest to the scheduled Study Time will be used. If there are two observations equidistant to the scheduled Study Time, the later observation will be used. The size of difference from the Study Time will be determined based on the number of days after administration.

Among the evaluation points, at the end of administration, the data with the largest number of days after administration will be used among the evaluable data within the visit window.

MDS-UPDRS Part I, II, III, and IV Total Scores, MDS-UPDRS Part II + Part III Total Score, MDS-UPDRS Tremor, Muscle Rigidity, and Akinesia/Bradykinesia Scores, and MDS-UPDRS Individual Scores

Visit	Scheduled Study Time	Visit Windows	
		Number of days after administration	Number of days after the end of administration
Baseline (prior to TVP-1012 administration)	Number of days after administration: -1	-22 ~ -1	
Week 6	Number of days after administration: 42	1 ~ 55	< 8
Week 10	Number of days after administration: 70	56 ~ 83	< 8
Week 14	Number of days after administration: 98	84 ~ 118	< 8
Week 20	Number of days after administration: 140	119 ~ 160	< 8
Week 26	Number of days after administration: 182	161 ~ 202	< 8
Week 32	Number of days after administration: 224	203 ~ 237	< 8
Week 36	Number of days after administration: 252	238 ~ 265	< 8
Week 40	Number of days after administration: 280	266 ~ 300	< 8
Week 46	Number of days after administration: 322	301 ~ 342	< 8
Week 52	Number of days after administration: 364	343 ~ 385	< 8
At end of administration		1 ~ 385	< 8

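### In the P -> 1 mg group, ECG, weight and PDQ-39 values from subjects who stop in the first 12 weeks on TVP-1012 are reported as Week 14, and ECG and weight have no end-of-administration row

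*Protocol*

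**What the plan says.** **Early termination.** Protocol section 9.3.3 applies "For subjects who started the investigational drug administration in this study and are withdrawn from the study before the last visit at Week 52". For them, "the procedures scheduled at Week 52 should be performed within 7 days from the termination of study medication", whenever possible. The list includes weight, ECG and the QOL questionnaire (PDQ-39). Appendix A of the protocol schedules these three measures at VISIT 8, VISIT 12 and VISIT 14 only.

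**Windows.** In the SAP's Definition of Visit Window, part A, the PDQ-39 table and the 12-lead ECG and weight table have the same four windows: Week 14 is Day 1 to 139, Week 26 is 140 to 230, Week 40 is 231 to 321, and Week 52 is 322 to 385. All require fewer than 8 days since the end of administration. At these points "evaluable data within the visit window will be used", with no restriction to scheduled visits. If there are several values, "the examinations, observation, and assessments with the Study Time closest to the scheduled Study Time will be used".

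**Day 1.** The SAP Glossary counts from the "day of first study drug administration for the treatment period in the preceding study" for 1 mg -> 1 mg, and from the "day of first study drug administration in this study" for P -> 1 mg. Protocol section 6.1 adds: "Subjects will start dosing from the day after the VISIT 8".

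**Reported rows.** PDQ-39 (SAP 2.2.2) has an end-of-treatment row in addition to the four visits. ECG (SAP 3.2.2.2) and weight (SAP 3.2.2.3) have only baseline and the four visits, plus case plots. ECG interpretation has a shift table over the same visits.

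**The concern.** A P -> 1 mg subject who stops after ten days has an ECG, a weight and a questionnaire at about that time, and the SAP tabulates them as Week 14 on TVP-1012. The Week 14 row is the first on-treatment row for all three measures, so it mixes values after 14 weeks of drug with last values after much shorter exposure. Any change that accumulates with treatment would look smaller than it is.

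ECG and weight are secondary safety endpoints in a study whose primary objective is long-term safety, and for them there is a second effect. With no end-of-administration row, a P -> 1 mg early-termination value up to Day 139 either carries the Week 14 label or, if a scheduled value lies closer to Day 98, drops out of the by-visit statistics and the ECG shift table. The same loss can occur in 1 mg -> 1 mg: a stop before Day 231 competes with VISIT 8 in the Week 26 window, and VISIT 8 is usually closer to Day 182. Vital signs have an overall table of markedly abnormal values as a backstop (SAP Appendix 2); ECG and weight have none.

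**Working it through.** 1. **Reproduce the SAP's cuts.** Midpoints between scheduled days are (98+182)/2 = 140, (182+280)/2 = 231 and (280+364)/2 = 322. These are the first days of the Week 26, 40 and 52 windows, as stated. The lower limit of the Week 14 window is not a midpoint; it is set at Day 1. The window therefore reaches 97 days below and 41 days above the nominal Day 98.

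2. **Place VISIT 12 on the P -> 1 mg clock.** Dosing starts the day after VISIT 8, so TVP-1012 day = study day − VISIT 8 study day. Appendix A allows VISIT 8 on Days 175 to 189 and VISIT 12 on Days 273 to 287. The earliest VISIT 12 is 273 − 189 = Day 84, the latest is 287 − 175 = Day 112, and the nominal one is 280 − 182 = Day 98. Before Day 84 there is no scheduled on-drug value of the three measures to compete with an early-termination value.

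3. **Place 1 mg -> 1 mg early terminations.** With VISIT 8 on Day 175 at the earliest, the first extension dose is on Day 176. Early-termination values from the extension therefore fall on Day 176 or later, in the Week 26, 40 or 52 windows and never in Week 14.

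4. **Planned stops in P -> 1 mg.** Protocol section 13.3 gives about 182 enrolled and 155 treated for 26 weeks. Assume an equal split, 182/2 = 91 per group. Assume also that the 155 includes all 91 subjects entering from the 1 mg arm, who already have 26 weeks of exposure. Then 155 − 91 = 64 P -> 1 mg subjects complete and 91 − 64 = 27 stop.

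5. **Values labelled Week 14.** Assume early-termination visits are uniform over 182 days and all are made:
   - Days 1 to 83: 27 × 83/182 = 12.3, or 13.5% of 91.
   - Days 1 to 48: 27 × 48/182 = 7.1, or 8% of 91.
   - Days 49 to 83: 27 × 35/182 = 5.2.
   - With 9 stops (about 10%, taken as a low case), Days 1 to 83: 9 × 83/182 = 4.1, or 4.5% of 91.

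6. **Understatement of a linearly building change at Day 98.** Linear build-up is an assumption. The mean day within 1 to 83 is 42, so the understatement is 0.135 × (1 − 42/98) = 0.077, about 8%. With 9 stops it is 0.045 × (1 − 42/98) = 0.026, about 3%.

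7. **After a Day 49 start.** The row keeps 91 − 7.1 = 83.9 subjects, of whom 5.2 (6.2%) stopped on Days 49 to 83, at mean day 66. The understatement becomes 0.062 × (1 − 66/98) = 0.020, about 2%.

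**The case against.** Several stronger readings are tempting, and the documents do not support them.

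- **That the SAP breaks its own window rule.** It does not. Every first post-baseline window starts at Day 1: Week 6 for MDS-UPDRS is 1 to 55, and Week 3 for laboratory tests and vital signs is 1 to 31. Midpoints govern only the interior cuts. What differs here is the reach: 97 days below nominal, against 41 (42 − 1) for MDS-UPDRS and 20 (21 − 1) for laboratory tests and vital signs.
- **That both groups are affected.** Section 9.3.3 covers only subjects dosed in this extension. A 1 mg subject who stopped in the preceding study could enter the Week 14 row, because the data are pooled, but that study's early-termination schedule is not in these documents. A count combining both groups would also match no planned table, since these summaries are given by preceding-study group.
- **That early stoppers' ECG and weight are hidden.** Case plots of observed values are planned for both. The gap is in the by-visit statistics and the ECG shift table.
- **That PDQ-39 is seriously diluted by placebo-period recall.** Subjects "assess QOL during 1 month prior to the day of the assessment", so a P -> 1 mg form before about Day 30 partly describes placebo weeks. That is about 27 × 30/182 = 4.5 forms, each only partly affected, on an additional endpoint that already has an end-of-treatment row.

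Two further points stand. Starting at Day 1 does keep early values in a by-visit row, so moving the start without adding an end row would lose them for ECG and weight. The Handling Rules for Analysis Data, which define evaluable values, are not available here and could narrow what enters the window; the SAP text as written does not.

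**Conclusion.** The point holds for P -> 1 mg and is of low severity. An early-termination ECG, weight or PDQ-39 value from Days 1 to 83 will normally be reported as Week 14. For ECG and weight, no other tabulated row shows a subject's last on-treatment value as such.

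On the planning figures this concerns about 12 of 91 subjects (13.5%), or about 4 (5%) if only 9 stop. The corresponding understatement of a linearly building change is about 8% or 3%. These sizes rest on 91 subjects per group, uniform dropout and every early-termination visit being made, although the protocol asks for it only whenever possible. The understatement also needs linear build-up, for which the documents give no basis. The summaries are descriptive and no hypothesis test depends on them. Section 9.3.3 of the protocol contains no error; the issue lies in the SAP windows and row lists.

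**What to change.** 1. Add an end-of-administration row (Day 1 to 385, fewer than 8 days after the last dose, latest evaluable value) to the ECG and weight window table and to the visit lists in SAP 3.2.2.2 and 3.2.2.3. This is the definition already used for MDS-UPDRS and PDQ-39.
2. With that row in place, start the Week 14 window for ECG, weight and PDQ-39 at Day 49, the midpoint of Day 0 and Day 98. This extends the interior-cut convention to the first window. No on-schedule P -> 1 mg VISIT 12 value is lost, since the earliest falls on Day 84.

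The cost is SAP wording and one more row in the ECG and weight outputs; no new data are collected. Under the 27-stop assumption the P -> 1 mg Week 14 N falls by about 7, with those values kept in the end-of-administration row. About 5 subjects who stop on Days 49 to 83 would still carry the Week 14 label; a footnote giving the range of actual days would make that visible.

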9.3.4 Post Study Care

The study medication will not be available upon completion of the subject's participation in the study.

10.0 PRETREATMENT EVENTS AND ADVERSE EVENTS

10.1 Definitions

10.1.1 PTEs

A PTE is defined as any untoward medical occurrence in a clinical investigation subject who has signed informed consent to participate in the preceding study but prior to administration of study medication of the run-in period of the preceding study; it does not necessarily have to have a causal relationship with study participation.

10.1.2 AEs

An AE is defined as any untoward medical occurrence in a clinical investigation subject administered a drug; it does not necessarily have to have a causal relationship with this treatment.

An AE can therefore be any unfavorable and unintended sign (e.g., a clinically significant abnormal laboratory finding), symptom, or disease temporally associated with the use of a drug whether or not it is considered related to the drug.

10.1.3 Additional Points to Consider for PTEs and AEs

An untoward finding generally may:

- Indicate a new diagnosis or unexpected worsening of a pre-existing condition. (Intermittent events for pre-existing conditions underlying disease should not be considered PTEs or AEs.)
- Necessitate therapeutic intervention.
- Require an invasive diagnostic procedure.
- Require discontinuation or a change in dose of study medication or a concomitant medication.
- Be considered unfavorable by the investigator for any reason.

Diagnoses vs signs and symptoms:

Each event should be recorded to represent a single diagnosis. Accompanying signs (including abnormal laboratory values or ECG findings) or symptoms should NOT be recorded as additional AEs. If a diagnosis is unknown, sign(s) or symptom(s) should be recorded appropriately as a PTE(s) or as an AE(s).

Laboratory values and ECG findings:

Changes in laboratory values or ECG parameters are only considered to be PTEs or AEs if they are judged to be clinically significant (i.e., if some action or intervention is required or if the investigator or sub-investigator judges the change to be beyond the range of normal physiologic fluctuation). A laboratory re-test and/or continued monitoring of an abnormal value are not considered an intervention. In addition, repeated or additional noninvasive testing for verification, evaluation or monitoring of an abnormality is not considered an intervention.

If abnormal laboratory values or ECG findings are the result of pathology for which there is an overall diagnosis (e.g., increased creatinine in renal failure), the diagnosis only should be reported appropriately as a PTE or as an AE.

Pre-existing conditions (disease or symptom present before signing of the informed consent in the preceding study):

Pre-existing conditions (present at the time of signing of informed consent in the preceding study) are considered concurrent medical conditions and should NOT be recorded as PTEs or AEs. Baseline evaluations (e.g., laboratory tests, ECG, X-rays etc.) immediately after signing of informed consent in the preceding study should NOT be recorded as PTEs unless related to study procedures. However, if a subject experiences an abnormality (e.g., internal bleeding due to blood collection) related to the procedures for the baseline tests/observations in the preceding study, the abnormality should be recorded as a PTE on the (e)CRF. If the subject experiences a worsening or complication of such a concurrent condition, the worsening or complication should be recorded appropriately as a PTE (worsening or complication occurs before start of study medication) or an AE (worsening or complication occurs after start of study medication). The investigator or sub-investigator should ensure that the event term recorded captures the change in the condition (e.g., “worsening of hypertension”).

If a subject has a pre-existing episodic condition (e.g., asthma, epilepsy) any occurrence of an episode should only be captured as a PTE/AE if the episodes become more frequent, serious or severe in nature, that is, the investigator or sub-investigator should ensure that the AE term recorded captures the change in the condition from Baseline (e.g. “worsening of...”). If a subject has a degenerative concurrent condition (e.g., cataracts, rheumatoid arthritis), worsening of the condition should only be captured as a PTE/AE if occurring to a greater extent to that which would be expected. Again, the

CONFIDENTIAL

investigator or sub-investigator should ensure that the AE term recorded captures the change in the condition (e.g., “worsening of...”).

Worsening of PTEs or AEs:

If the subject experiences a worsening or complication of a PTE after starting administration of the study medication, the worsening or complication should be recorded appropriately as an AE. Investigators should ensure that the AE term recorded captures the change in the condition (e.g., worsening of...”).

If the subject experiences a worsening or complication of an AE after any change in study medication (including change from a study medication for the CCT-001 study to that for the OCT-001), the worsening or complication should be recorded as a new AE. Investigators should ensure that the AE term recorded captures the change in the condition (e.g., worsening of...”).

Changes in severity of AEs /Serious PTEs:

If the subject experiences changes in severity of an AE/serious PTE, the event should be captured once with the maximum severity recorded.

Preplanned surgeries or procedures:

Preplanned procedures (surgeries or therapies) that were scheduled prior to signing of informed consent in the preceding study are not considered PTEs or AEs. However, if a preplanned procedure is performed early (e.g., as an emergency) due to a worsening of the pre-existing condition, the worsening of the condition should be captured appropriately as a PTE or an AE. Complications resulting from any planned surgery should be reported as AEs.

Elective surgeries or procedures:

Elective procedures performed where there is no change in the subject’s medical condition (e.g., cosmetic surgery) should not be recorded as PTEs or AEs, but should be documented in the subject’s source documents. Complications resulting from an elective surgery should be reported as AEs.

Insufficient clinical response (lack of efficacy):

Insufficient clinical response, efficacy, or pharmacologic action, should NOT be recorded as an AE. The investigator or sub-investigator must make the distinction between exacerbation of pre-existing illness and lack of therapeutic efficacy.

Overdose:

Cases of overdose with any medication without manifested side effects are NOT considered PTEs or AEs, but instead will be documented on an Overdose page of the (e)CRF. Any manifested side effects will be considered PTEs or AEs and will be recorded on the AE page of the (e)CRF.

